Group-based approaches for dietary education compared to individual dietary counselling has also been found to improve dietary habits (34), and structured group education programs in carbohydrate counting can improve glycaemic control, self-management skills and quality of life in patients with T1D (32, 35) which in turn could lead to better clinical outcomes.

At Steno Diabetes Center Copenhagen (SDCC) patients with T1D have been offered a structured, non-randomized group education program in BCC since 2013. Interestingly, data from completers of these education programs indicate that participation improved their carbohydrate counting skills ($p<0.001$), reduced HbA1c ($p=0.02$) and body weight (non-significant) after six months when compared to baseline (unpublished data). Participants also reported increased knowledge concerning types and amounts of carbohydrates and on how to prevent hyper- and hypoglycaemia. At Copenhagen University hospital Hvidovre patients with T1D on MDI therapy have been offered structured group education program in ACC including an automated bolus calculator (the BolusCal training concept) for several years. Recently the Hvidovre group published a (non-randomized) study demonstrating that short-term intensive training in this concept reduced HbA1c by 9 mmol/mol after 12 months when compared to baseline ($p<0.001$) (36).

Although the initial results are promising, additional research using a RCT approach is needed to assess the efficacy of BCC and ACC compared to a control learning situation. The current study is designed to evaluate the effectiveness of two different group-based dietitian-led dietary self-management approaches compared to standard nutrition education on glycaemic control in patients with T1D. The BCC concept aims at improving carbohydrate counting accuracy and day-to-day consistency of carbohydrate intake (the BCC intervention) and the concept of ACC aim at improving prandial insulin dose accuracy using an automated bolus calculator (the ABC-ACC intervention).

7 Main hypotheses

1. Training and education in the BCC concept will reduce HbA1c or the average glucose variability more than standard nutrition education (control). Nutrition education in BCC will improve patients' knowledge and awareness of carbohydrate amounts, improve carbohydrate estimating accuracy together with focus on reduced variability in the carbohydrate intake which will reduce the glucose variability and possibly also improve HbA1c.

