2. Training and education in the ABC-ACC concept will reduce average glucose variability and HbA1c more than standard nutrition education (control). An accurate calculation of each patient's prandial insulin needs and assistance of a bolus calculator for calculating prandial insulin dose to reach a specific postprandial glucose target is more precise.
3. There are no differences in glycaemic effects between patients receiving training and education in the BCC concept versus the ABC-ACC concept. However, subgroups of patients with T1D may benefit more from the BCC concept compared to the ABC-ACC and vice versa (cf. sub-hypotheses).

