7.1 Sub-hypotheses

- BCC can be used to improve glycaemic control in patients with infrequent and limited (1-2 times/day) monitoring of plasma glucose values, if adherence to a guiding personalized carbohydrate plan is high
- Participants with low mathematical literacy will have greater improvements in glycaemic control practicing the BCC concept compared to the ABC-ACC concept due to a simpler educational meal plan approach focusing on training skills in estimating carbohydrate amounts and use of a guiding personalized carbohydrate meal plan
- Practising the ABC-ACC concept will improve the glycaemic control more than practising the BCC concept due to a more accurate dosing of meal insulin taking into account C:I ratios, insulin sensitivity factor active meal insulin
- Practicing ABC-ACC may induce weight gain, deleterious changes in body composition or lipidemic control due to higher flexibility in eating in terms of food choices thereby increasing the energy intake
- Diet-related quality of life may be higher using the ABC-ACC concept compared to the BCC concept due to a higher flexibility when practicing ABC-ACC, while participants' diet-related quality of life may drop in the BCC group due to a more rigorous dietary regimen aiming at eating a relatively fixed amount of carbohydrates at meals inducing a feeling of less freedom to eat as one wish
- Greater perceived competencies and support for autonomy will lead to improved glycaemic control through improved diabetes self-management
- Objective measurements of dietary adherence may improve the possibility of proving clinical effects of either the BCC or ABC-ACC concept in participants with high dietary adherence

8 Objectives

The overall objective is to compare the effect of two different nutritional programs (BCC and ABC-ACC) with the routine outpatient nutritional education on glycaemic control (HbA1c and plasma glucose variability) in adult patients with T1D after 6 months of intervention.

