### Hypotheses for the primary outcomes:

1. We hypothesize that ACC is superior compared with usual dietary care (the control group) in reducing HbA1c or MAGE from baseline to end-of-treatment at week 24 (from V1 to V2).

Superiority is claimed if:

- a. the 95% confidence interval for the estimated difference in change between the groups for HbA1c or MAGE, estimated using a baseline corrected linear mixed model, excludes 0 and the P-value is <0.05: and,
- b. the estimated difference in HbA1c or MAGE between the two groups is equal to/surpass the minimal important difference in favour of the ACC group.

2. We hypothesize that BCC is superior compared with usual dietary care (control group) in reducing HbA1c or MAGE from baseline to end-of-treatment at week 24 (from V1 to V2).

Superiority is claimed if:

- c. the 95% confidence interval for the estimated difference in change between the groups for HbA1c or MAGE, estimated using a baseline corrected linear mixed model, excludes 0 and the P-value is <0.05: and,
- d. the estimated difference in HbA1c or MAGE between the two groups is equal to/surpass the minimal important difference in favour of the BCC group.

3. We hypothesize that BCC is equivalent to ACC in reducing HbA1c or MAGE from baseline to end-of-treatment at week 24 (from V1 to V2).

Equivalence is claimed if:

- e. The 90% confidence interval for the estimated difference in change between the groups for HbA1c or MAGE does not surpass minimal important difference in a negative or positive direction (16).

Hypotheses for the secondary outcomes can be found in the study protocol and [clinicaltrials.gov](https://clinicaltrials.gov).

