## Section 4: Statistical Principles

### Confidence intervals and P values

Two-sided P-values and 95% confidence intervals will be presented for comparisons between groups. Two-sided 95% confidence intervals will be presented for within group comparisons and estimated levels.

**Primary outcome:** The direction and size of the estimated mean effect for HbA1c and MAGE (primary outcomes), in addition to the 95% confidence intervals, will be required to support the tested hypotheses for the results to be declared in accordance with the hypotheses (see section 2 under “Objectives”).

**Secondary outcomes:** False detection rate (FDR) correction ad modum Benjamini and Hochberg (17) will be used to control for multiplicity; < 5% will be used as the threshold for FDR.

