## Section 6: Analysis

### Outcome definitions

#### **Primary outcomes**

HbA1c and MAGE. The treatment effect will be given as the baseline corrected difference in mmol/mol for HbA1c and mmol/l for MAGE between the ACC versus the control group, and the BCC versus the control group at V2.

Estimation of minimal important difference for primary outcome: Reductions in HbA1c of 3.5 mmol/mol and 0.35 mmol/l of MAGE were defined as minimal important differences in this trial. This was based on findings from experimental studies examining the HbA1c effect of BCC (19-21), and meta-analyses of RCTs examining the HbA1c effect of ACC (13-14) vs. control or usual dietary treatment. In these studies, HbA1c reductions between 3 to 7 mmol/mol had been found in adults with T1D. All participants in the studies had a more poorly controlled diabetes (60-108 mmol/mol) than participants eligible for inclusion in our study (53-97 mmol/mol). Consequently, we expected to find smaller HbA1c reductions in our study population. This was considered clinically relevant as part of a multidisciplinary approach for improving glycaemic control in T1D.

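### SAP criterion (e) does not confine a BCC–ACC equivalence claim to the outcome that met its margin, and SAP Section 4 states a different rule

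*SAP*

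**What the plan says.** SAP Section 2, hypothesis 3, reads: "We hypothesize that BCC is equivalent to ACC in reducing HbA1c or MAGE from baseline to end-of-treatment at week 24". Criterion (e) then says that equivalence is claimed if "The 90% confidence interval for the estimated difference in change between the groups for HbA1c or MAGE does not surpass minimal important difference" in either direction. The conclusion names no outcome, and nothing says what follows if the other outcome fails.

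Four other places bear on the rule:

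- **SAP Section 6, Primary outcomes**, gives each outcome its own margin: "Reductions in HbA1c of 3.5 mmol/mol and 0.35 mmol/l of MAGE were defined as minimal important differences in this trial". It defines the primary treatment effects only as ACC versus control and BCC versus control.
- **SAP Section 4, Confidence intervals and P values**, says that the sign and magnitude of the estimates for "HbA1c and MAGE (primary outcomes), in addition to the 95% confidence intervals, will be required to support the tested hypotheses". It refers back to Section 2 and does not mention a 90% interval.
- **Protocol sections 8.1 and 9.1.1** (primary objective and primary outcome) join HbA1c and MAGE with 'or', as the SAP hypotheses do.
- **Protocol section 7, hypothesis 3**, is broader: "There are no differences in glycaemic effects between patients receiving training and education in the BCC concept versus the ABC-ACC concept".

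Criteria (a)–(d), for the two superiority hypotheses, also use 'or', and repeat it separately in the significance condition and in the minimal-important-difference condition.

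**The concern.** For superiority, a win on either outcome is at least a coherent finding. Equivalence is a statement that no important difference exists, so a pass on one outcome can stand beside a clear difference on the other. If the report then says without qualification that BCC is equivalent to ACC, the sentence says more than the data show.

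The documents admit three rules: either outcome suffices, each outcome carries its own claim, or both must pass. The interval level is also unsettled, because criterion (e) uses 90% and Section 4 uses 95%. If the choice among these is made after the results are known, that conclusion is not prespecified.

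Criteria (a)–(d) have a related gap. Read literally, the interval and P-value condition could be met by one outcome and the minimal-important-difference condition by the other.

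**Working it through.** **Inputs.** Protocol section 13.3: 64 evaluable per arm (77 enrolled), SD 7 mmol/mol for HbA1c and 0.7 mmol/l for MAGE. SAP Section 6: margins 3.5 and 0.35. The correlation between the two estimates is not given, so 0 to 0.7 is assumed.

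**1. The plan's own figure.** A two-sided 5% t-test for a difference of 3.5 with SD 7 needs 63.8 per arm, rounded up to 64, with power 80.1%. This reproduces the plan. It concerns superiority over control; no power or error rate is stated for equivalence.

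**2. One outcome under the 90% interval rule.** SE = SD × √(2/n) = 7 × √(2/64) = 1.237. The 90% half-width is about 1.645 × 1.237 = 2.04, so the estimate must lie within about 3.5 − 2.04 = 1.46 of zero. MAGE scales identically (half-width 0.204). With an estimated SE and t quantile, the chance of passing is 0.757 at a true difference of 0, 0.401 at half the margin and 0.050 at the margin.

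**3. The literal 'or' rule.** For independent outcomes, P(claim) = 1 − (1 − p₁)(1 − p₂). The ranges come from simulating 400,000 trials per cell over correlations 0 to 0.7.

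| True HbA1c, MAGE difference | Independent outcomes | Range |
|---|---|---|
| 3.5, 0.35 (both at margin) | 1 − 0.95 × 0.95 = 0.098 | 8–10% |
| 3.5, 0.175 | 1 − 0.95 × 0.599 = 0.43 | 41–43% |
| 3.5, 0 (extreme case) | 1 − 0.95 × 0.243 = 0.769 | 77–79% |

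**4. Sensitivity to the MAGE SD.** Protocol section 13.3 also reports an SD of 1.0 from an earlier carbohydrate counting trial. Then SE = 1.0 × √(2/64) = 0.177 and the half-width is about 0.291, which leaves 0.35 − 0.291 = 0.059. The MAGE pass probability is about 0.26, and the extreme case becomes about 1 − 0.95 × 0.74 = 0.30 (simulated 29–30%).

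**5. How much the choice of rule matters.** With identical arms and 64 per arm, the chance of an equivalence claim is:

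- either outcome, 90% interval: 1 − 0.243² = 0.94 if independent, range 88–94%;
- both outcomes, 90% interval: 0.757² = 0.57 if independent, range 57–63%;
- both outcomes, 95% interval: 0.603² = 0.36 if independent, range 36–43%.

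These claims would all be true. The figures show only that the unstated rule changes how often the claim is made.

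**The case against.** The strongest reply is that hypothesis 3 never says BCC is equivalent to ACC outright. It says equivalent in reducing HbA1c or MAGE. Criterion (e) speaks of one interval and one margin, Section 6 gives each outcome a margin in its own unit, and no composite exists. On that reading each outcome carries its own claim. The reply is plausible, but the SAP does not state it. Criterion (e) could also be read as requiring that neither interval cross its margin, and Section 4 points towards both outcomes, though at a different interval level. That several readings are defensible is itself the problem.

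Three stronger inferences are tempting and should not be drawn.

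- **That the plan would declare false equivalence in more than three quarters of trials.** In the extreme case MAGE truly is equivalent. The 77–79% is essentially the MAGE power of 0.757, and those claims mislead only if the outcome is left unnamed. The clear error inflation is 8–10% against 5%.
- **That the documents predict split results.** The only hint is that BCC education is expected to have effects "which will reduce the glucose variability and possibly also improve HbA1c", while ABC-ACC is expected to reduce both. No passage predicts a BCC–ACC HbA1c gap of 3.5 with no MAGE difference.
- **That the protocol requires both outcomes.** Its overall objective speaks of effects "on glycaemic control (HbA1c and plasma glucose variability) in adult patients with T1D after 6 months of intervention", but sections 8.1 and 9.1.1 use 'or', and 8.1 ties glycaemic control to HbA1c and names MAGE as the alternative.

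It also stands that the trial is framed as a superiority trial, and that SAP Section 6 has between-group differences with intervals extracted for the continuous outcomes, so a split result would be visible.

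**Conclusion.** The point holds as a minor defect in a decision rule. Criterion (e) does not tie the equivalence claim to the outcome that passed, and Section 4 conflicts with it on both the connective and the interval level.

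An unqualified claim under the literal rule carries an 8–10% false-equivalence rate with both true differences at the margin, against 5% for one outcome. The larger figure for the extreme case measures exposure to a badly worded conclusion and is not an error rate under the outcome-by-outcome reading. These sizes rest on 64 evaluable per arm, the protocol's planning SDs and an assumed correlation of 0 to 0.7. The extreme case is sensitive to the MAGE SD.

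The consequence is confined to how one of three primary conclusions is worded, since both differences and their intervals are reported.

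**What to change.** Before analysis, amend the SAP wording as follows.

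- **Criterion (e):** judge and claim equivalence separately for each outcome, against its own margin, using the 90% interval, and name the outcome in the conclusion (equivalent on HbA1c; equivalent on MAGE). Any unqualified statement that BCC is equivalent to ACC requires both to pass.
- **Section 4:** state the same rule, and say that equivalence uses the 90% interval.
- **Criteria (a)–(d):** use the same outcome-specific wording, so that the interval, P-value and minimal-important-difference conditions must all be met by the same outcome.

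No new data are needed. Outcome-specific equivalence claims lose no power: with identical arms, 76% per outcome at 64 per arm and 85% at 77. The unqualified statement, if wanted, would be reached in 57–63% at 64 per arm and 72–77% at 77. If outcome-by-outcome claims were always intended, the change to (e) mainly records that.

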## Section 3: Study Methods

### Trial design

Single-centre parallel-group, randomised controlled, open-label, superiority trial. Allocation ratio 1:1:1 to either ACC, BCC, or control (usual dietary management).

### Randomisation

Participants were randomised using block randomisation by stratifying participants based on sex and HbA1c at baseline. The randomization list was generated by an external statistician and uploaded to the electronic data management system REDCap (8.10.18, Vanderbilt University, TN, USA). Participants eligible for inclusion in the study according to the screening were randomised at the end of the screening visit (V0) by the study investigator/study personnel using the randomization module in REDCap. Baseline measurements were collected at the following baseline visit (V1) for all participants.

### Sample size

See study protocol.

### Framework

Superiority trial. See Objectives section.

### Statistical interim analyses and stopping guidance

No interim analyses were planned and no guidelines for terminating the trial early was made.

### Timing of final analyses

The results will be analysed when this statistical analysis plan has been uploaded at [clinicaltrials.gov](https://clinicaltrials.gov)

### Timing of outcome assessments

HbA1c was measured at the screening visit (V0), at the baseline visit (V1), after 12 weeks of intervention, after 24 weeks (V2) of intervention, and after six months follow-up (V3). MAGE was measured after the baseline visit (V1), and after 24 weeks of intervention (after V2).

See section 6: Analyses for timing of secondary/descriptive/explorative outcome assessments.

## Section 4: Statistical Principles

### Confidence intervals and P values

Two-sided P-values and 95% confidence intervals will be presented for comparisons between groups. Two-sided 95% confidence intervals will be presented for within group comparisons and estimated levels.

**Primary outcome:** The direction and size of the estimated mean effect for HbA1c and MAGE (primary outcomes), in addition to the 95% confidence intervals, will be required to support the tested hypotheses for the results to be declared in accordance with the hypotheses (see section 2 under “Objectives”).

**Secondary outcomes:** False detection rate (FDR) correction ad modum Benjamini and Hochberg (17) will be used to control for multiplicity; < 5% will be used as the threshold for FDR.

### Completers and protocol deviations

**Completers:** Participants who participated in an assessment of at least one of the primary outcomes at V2 and/or V3.

**Lost to follow-up:** Participants who did not participate in assessment of primary outcomes at V2.

**Excluded for statistical data analyses:** Participants in the three study groups dropping out or lost to follow-up before baseline measurements have been collected.

**Protocol deviators:** None of the participants in the two study groups are considered protocol deviators.

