### Analysis populations

Efficacy estimates based on intention-to-treat (ITT) analysis set:

All participants will be analysed as randomised.

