### **Other outcomes**

- Number of visits with dietitians, endocrinologists, and diabetes nurses at V2 and V3 in each group.
- Use of bolus calculator to assist insulin dose decision-making in the ACC arm collected after V2.
- Self-reported use of tools to estimate carbohydrate amounts in meals for each group at V1, V2, V3.
- Self-reported frequency and method for estimating mealtime insulin dose for each group at V1, V2, V3.
- Supplementary table with baseline characteristics for completers vs. non-completers with dropout before V2
  - Number of participants, n
  - Age (years)
  - Gender, male, n and %
  - Current smokers, n and %
  - Self-reported educational level
    - o Elementary school, n and %
    - o Upper secondary education, n and %
    - o Vocational, n and %
    - o Short further (< 3 y), n and %
    - o Medium further (3-4 y), n and %
    - o Long further (> 4 y), n and %
    - o Other education, n and %
  - Living alone, n and %
  - Body weight (kg)
  - BMI (kg/m^2)
  - Diabetes duration (years)
  - HbA1c (mmol/l)
- Supplementary table with extra baseline characteristics
  - Occupation
    - o Employed/self-employed, n and %
    - o Unemployed / job seeking, n and %
    - o Retired, n and %
    - o Other (on leave / studying), n and %
  - Annual household income (before tax)
    - o < 100,000 DKK (<13,500 EUR)
    - o 100,000 – 200,000 DKK (13,500 – 27,000 EUR)
    - o 200,000 – 400,000 DKK (27,000 – 54,000 EUR)
    - o 400,000 – 600,000 DKK (54,000 – 81,000 EUR)
    - o 600,000 – 800,000 DKK (81,000 – 108,000 EUR)
    - o 800,000 DKK (>108,000 EUR)
    - o Unspecified
  - Waist circumference, cm (women)
  - Waist circumference, cm (men)

- Fasting concentration of plasma lipids
  - o Total cholesterol (mmol/l)
  - o HDL cholesterol (mmol/l)
  - o Triglycerides (mmol/l)
- Dietary intake
  - o Total energy, kJ/day (women)
  - o Total energy, kJ/day (men)
  - o Carbohydrates, g/day (men)
  - o Carbohydrates, g/day (women)
  - o Carbohydrates, E%
- Physical activity level
  - o Low, n and %
  - o Moderate, n and %
  - o High, n and %
- Supplementary table with baseline-adjusted estimates for other secondary/exploratory outcomes
  - Glycaemic variability, standard deviation (SD), mmol/l
  - Average waist, cm
  - Fasting concentration of plasma lipids
    - o Total cholesterol (mmol/l)
    - o HDL cholesterol (mmol/l)
    - o Triglycerides (mmol/l)
  - Numeracy skills test, correct answers, %
  - Dietary intake (not measured at V3)

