## Analysis methods

Analyses of the primary outcomes will be performed based on efficacy estimates.

Before further analysis and before unblinding, all variables will be inspected to detect outliers to uncover potential errors, such as registration errors.

All continuous outcomes covered by this SAP will as a rule be modelled using baseline corrected repeated measures regression (22) with the following fixed effects and interactions between fixed effects: Visit, Visit (factorial)\*Treatment. Data from V1, V2, and V3 will be included in the analysis. The models will be specified with a restricted maximum likelihood estimation method and a repeat on participant level (unstructured covariance structure). Model fit will be evaluated using graphical methods before estimating the treatment effects and if necessary, outcomes will be log-transformed. Estimated mean differences (CI95%) between groups (CI95%), conditional means (CI95%), and within group changes (CI95%) will be extracted from the model. For log-transformed outcomes the results will be back-transformed and be presented as the ratio between estimated mean differences (CI95%), estimated conditional geometric means (CI95%) and relative changes within groups (CI95%), respectively. If log-transformation cannot meet distribution assumptions, a generalized mixed linear model with an appropriate distribution will be applied instead of the repeated measures regression model. In case the distribution does not comply with the distributions available in the generalized mixed linear model a non-parametric test will be used to compare the change scores for the given outcome.

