## Missing data

The number/frequency of missing values for the primary outcomes in each group at each time point will be provided. In the primary analysis, missing data are handled implicitly by maximum likelihood estimation in the linear mixed model and missing data will be assumed to be missing at random. This is equivalent to making multiple imputations for each treatment group separately and estimating the treatment effect that would have been found had all subject completed their assigned treatment (efficacy estimate) under the missing at random assumption.

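### The SAP's analysis set is modified ITT, although it is labelled ITT with everyone analysed as randomised, and the model omits the stratification factors sex and screening HbA1c

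*SAP*

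**What the plan says.** **Order of events.** The SAP (Randomisation) reports in the past tense that eligible participants "were randomised at the end of the screening visit (V0) by the study investigator/study personnel", with baseline collected at the following visit, V1. Allocation was stratified "by stratifying participants based on sex and HbA1c at baseline". SAP Timing of outcome assessments records HbA1c at V0 and again at V1.

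**Analysis set.** SAP Completers and protocol deviations excludes from the analyses "Participants in the three study groups dropping out or lost to follow-up before baseline measurements have been collected". The next section, Analysis populations, names the set ITT and adds "All participants will be analysed as randomised".

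**Model.** SAP Analysis methods fits a baseline-corrected repeated-measures model with visit and visit-by-treatment terms: "Data from V1, V2, and V3 will be included in the analysis". Neither sex nor V0 HbA1c appears. SAP Missing data describes the target as "estimating the treatment effect that would have been found had all subject completed their assigned treatment".

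**Protocol.** Section 13.2 makes ITT primary and states no such exclusion. Section 9.5.3 says that withdrawn participants are followed up at the end of the study and their data used if they allow it.

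**The concern.** Someone who reads that the set is ITT and everyone is analysed as randomised will assume that no allocated person was removed. The SAP's own exclusion says otherwise. The trial is open-label, so a participant could leave after learning the allocation and before V1, and such losses need not be balanced across arms.

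The model raises a second, separate point. When allocation is stratified, the usual practice is to analyse by the factors that were used. Under the SAP's order, the only HbA1c in existence at allocation was the V0 value. The model does correct for HbA1c, but with the later V1 measurement, and it leaves sex out.

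**Working it through.** **1. Does the exclusion remove randomised people?** This depends on when randomisation took place, and the documents disagree.

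| Place | Randomisation |
|---|---|
| SAP Randomisation | end of V0, before baseline |
| Protocol 11.2 | at screening, before the participant goes home |
| Protocol Table 1 | Screening column |
| Protocol 9.6 | at V1; on one route screening is also at V1 |
| Protocol 9.8 | at V1, after the baseline examination |
| Protocol section 10 | after the V1 baseline measurements |

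Protocol 12.2 also treats a V1 HbA1c as part of screening. The SAP is written in the past tense and agrees with 11.2 and Table 1, so I take its order as the working assumption. The exclusion's wording points the same way, because it refers to people already in the three study groups. On that order the exclusion contradicts the ITT statement. If everyone was randomised at V1 after baseline, it removes almost nobody who had been randomised.

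**2. Can the exclusion change the estimate?** V1 is one of the repeated responses in the model, so a missing V1 does not by itself stop a person from contributing.
- No value at V1 or later: the person adds nothing, whichever set is named.
- A later value despite leaving before V1: the person would contribute, and the exclusion discards the value. Follow-up under protocol 9.5.3 is at the end of the study, so it informs week 24 mainly through the correlation between visits.

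**3. How large would selective loss have to be?** Protocol 13.3 gives 64 per arm for 80% power (difference 3.5 mmol/mol, SD 7, two-sided 5%). A two-sample t-test calculation gives 63.8, so the 64 reproduces. Enrolment is 77 per arm, which leaves room for 77 − 64 = 13 losses per arm. The number lost before V1 is not given.

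Suppose k of 77 are lost before V1 in one arm and none in the other, and their unseen change differs from the rest by g. The contrast then moves by k × g / 77. To move it by 0.35 (10% of 3.5, a yardstick I chose), g = 0.35 × 77 / k:

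| k | g (mmol/mol) |
|---|---|
| 1 | 27.0 |
| 4 | 6.7 |
| 8 | 3.4 |
| 13 | 2.1 |

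The last row puts one arm's entire loss allowance before V1 and none in the other arm, so it is an extreme case.

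**4. What do the stratification factors add for HbA1c?** Only the SD of change (7) and 64 per arm come from the protocol. I assume an HbA1c SD of 9 at each visit, a V0–V1 correlation of 0.85 and a V0–week 24 correlation of 0.66 (range 0.60 to 0.69).
- V1–week 24 correlation: 1 − 49/(2 × 81) = 0.698.
- SE with V1 only: 9 × √(1 − 0.698²) × √(2/64) = 1.14.
- SE ratio with V0 added: 0.984 (1.000 to 0.966 over the range).
- Chance that the 95% CI excludes 0 at a true difference of 3.5: 87% with V1 only, 88% with V0 added.

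These formulas ignore the cost of estimating extra coefficients. In 6,000 simulated trials of 64 per arm, with sex assumed unrelated to outcome, adding V0 and sex gave SE ratios of 1.01, 0.99 and 0.97 at V0–week 24 correlations of 0.60, 0.66 and 0.69. No corresponding calculation was made for MAGE.

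**The case against.** The strongest reply is that this is mostly a matter of wording. The SAP states the exclusion openly, immediately before the ITT statement. Its Recruitment section reports losses and exclusions after randomisation by group with reasons. Its Withdrawal/follow-up section puts the number lost in each group during each phase in the CONSORT diagram. The stated exclusion is therefore not concealed, and most losses before V1 will be visible by arm. This stands. What reporting does not do is make the set ITT, or bring back a later value that the exclusion drops. The "Supplementary table with baseline characteristics for completers vs. non-completers with dropout before V2" is not described as split by arm, and the SAP does not say whether losses before V1 are in it.

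It can also be said that V1 HbA1c already carries most of what V0 would add. That stands too: the gain is about one percentage point of power, and at the low end of the assumed range there is a slight loss.

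A reader might infer that correcting for a V1 value taken after allocation biases the result and that adding V0 cures this. The documents support neither step. V1 precedes all teaching (protocol 11.3 and 11.4), and nothing indicates that V1 shifted by arm. If it did shift by 1 mmol/mol in one arm, and arm means are constrained equal at V1 (which the SAP does not state), the estimate would move by 0.70. With V0 added it would still move by (0.698 − 0.66 × 0.85)/(1 − 0.85²) = 0.49. Matching the analysis to the design is the reason to add V0; it is not a cure for bias.

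**Conclusion.** The contradiction is in the current text. Under the SAP's order of events, the set is modified ITT and the statement that everyone is analysed as randomised is incorrect. The omission of sex and V0 HbA1c from the model is equally clear. Both should be fixed.

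A reader might go further and conclude that the primary result is biased or that differential dropout is concealed. The documents do not support that. They give no number lost before V1, people without later data cannot affect the model, and losses by group and phase are to be reported. The effect on the estimate is unknown, probably small and possibly zero.

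The first point, and the choice of which HbA1c to use in the second, assume randomisation at V0. If some participants were randomised at V1, the exclusion issue does not apply to them and V1 is their pre-allocation value. The precision figures rest on assumed correlations and concern HbA1c only.

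**What to change.** 1. **Analysis set.** Delete the exclusion, so that every randomised participant with any outcome value at V1 or later is analysed in the allocated arm, including withdrawn participants whose follow-up may be used under protocol 9.5.3. If the exclusion is kept, call the set modified ITT and remove the statement that all are analysed as randomised.
2. **Model.** Add sex and the HbA1c used for stratification (V0 under the SAP's order) as fixed effects by visit, and keep V1 in the model.
3. **Timing.** Reconcile protocol 9.6, 9.8, section 10 and 12.2 with protocol 11.2, Table 1 and SAP Randomisation. If more than one order was used, give the number randomised under each.

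Reporting the V0-to-V1 HbA1c change by arm, and an HbA1c sensitivity model with arm means constrained equal at V0, are optional.

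The cost is a few sentences in the SAP and two variables already collected. The expected change in the HbA1c standard error runs from about 3% better to about 1% worse.
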